12.1.4 Visit 14 (End-of-Study visit/85d or early completion)

The following tests will be conducted at the End-of-Study visit or early completion (only in subjects with complete healing).

- ① Conduct the physical examination.
- ② As vital signs, measure blood pressure, pulse, and body temperature.
- ③ Measure body weight.
- ④ Conduct laboratory tests (hematology, blood chemistry).
- ⑤ After removing the investigational device, take a photograph of the study ulcer, conduct the investigator's photo evaluation, and record the pressure ulcer size by a Scale and complete healing status.
- ⑥ Check the infection signs using the CSSC (Clinical Signs and Symptoms Checklist).
- ⑦ Conduct standard dressing.
- ⑧ After conducting the pressure ulcer assessment, record the PUSH score.
- ⑨ Review concomitant medication and adverse events (all adverse events, local adverse events at the study ulcer).
- ⑩ At the last visit, investigational devices that have been prescribed but not used are to be returned.
- ⑪ Based on the subject diary, record the frequency of self-dressing beyond once-weekly in the Case Report Form.

12.1.5 Unscheduled visit

In case it is necessary to conduct an unexpected and unscheduled visit due to reasons such as an adverse event, identify the purpose of the visit, review vital signs, adverse events and concomitant medication, and conduct laboratory tests, if necessary. There is no formal limitation in tests to be conducted during an unscheduled visit.

12.2 Methods for each study item

12.2.1 Demographic, medical history review

Before a subject enters into the study, the following subject background (demographic survey) and medical history information will be investigated with an interview, chart review, and questioning, and recorded in the Case Report Form.

- ① Demographic survey: Subject's initial, age, sex, etc.
- ② Medical history review: Pressure ulcer size/stage, pressure ulcer onset date and illness duration, current illnesses other than the study indication, hypersensitivity to drugs including similar prior medications, smoking status, smoking level, etc.
- ③ Concomitant medication/treatment survey: Current medication or concurrent treatment
- ④ Other disease history review: Prior surgical history of the target pressure ulcer, prior irradiation history of the target pressure ulcer over the past year, life expectancy, malnutrition status, alcohol or drug addiction status, etc.
- ⑤ Mobility: Mobility and condition of the subject, such as whether the subject is ambulatory/stays sitting only/stays lying only/is capable of sitting or lying, etc.

12.2.2 Laboratory tests, urine hCG test

Laboratory test and urine hCF test will be conducted once at screening and at study completion/early completion.

- Sample collection and documentation: Blood samples are collected from subjects according to the test schedule using an aseptic technique, and collected blood samples are analyzed in a QC-certified clinical pathology lab using commercialized hematology, blood chemistry test methods. Test findings are recorded in the Case Report Form and assessed for normal/abnormal status or clinical significance, and for clinically significant abnormal findings, the investigator's opinion will be recorded.
- Test parameters:
 - ① Hematology: WBC, RBC, WBC Differential count, hemoglobin, hematocrit, platelets
 - ② Blood chemistry: AST, ALT, ALP, creatinine, BUN, total bilirubin, glucose, protein, albumin, gamma GTP, TSH (TSH is conducted at screening only.)
 - ③ Urine hCG test (to be conducted in all women, except for those who have been menopausal for at least 1 year or had hysterectomy, bilateral oophorectomy, or bilateral salpingectomy)

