Pressure ulcer assessment ⁶ (digital photograph taking, investigator's photo evaluation) - Ulcer size (Using a scale) - Complete healing status	V ⁷	V	V	V	V	V	V	V	V	V	V	V	V	V	V	V	V	V	V	V	V	V	V	V	V	V

Item	Schedule	Screening		Treatment period																		Closing					
		1*	2*	3	4	5	6	7	8	9	10	11	12	13	14**												
		-14d~0d	1d (±1d)	5d* (±1d)	8d (±1d)	12d* (±1d)	15d (±1d)	19d* (±1d)	22d (±1d)	26d* (±1d)	29d (±1d)	33d* (±1d)	36d (±1d)	40d* (±1d)	43d (±1d)	47d* (±1d)	50d (±1d)	54d* (±1d)	57d (±1d)	61d* (±1d)	64d (±1d)	68d* (±1d)	71d (±1d)	75d* (±1d)	78d (±1d)	82d* (±2d)	85d (±2d)
PUSH		V			V				V				V				V			V							V
Self-dressing training		V		V	V	V	V	V	V	V	V	V	V	V	V	V	V	V	V	V	V	V	V	V	V	V	V
Dressing change frequency review				V	V	V	V	V	V	V	V	V	V	V	V	V	V	V	V	V	V	V	V	V	V	V	V
Infection sign checklist ⁸ (CSSC)		V		V	V	V	V	V	V	V	V	V	V	V	V	V	V	V	V	V	V	V	V	V	V	V	V
Subject diary distribution ⁹		V		V	V	V	V	V	V	V	V	V	V	V	V	V	V	V	V	V	V	V	V	V	V	V	V
Subject diary return				V	V	V	V	V	V	V	V	V	V	V	V	V	V	V	V	V	V	V	V	V	V	V	V
Concomitant medication/treatment review	V	V		V	V	V	V	V	V	V	V	V	V	V	V	V	V	V	V	V	V	V	V	V	V	V	V
Adverse event review		V		V	V	V	V	V	V	V	V	V	V	V	V	V	V	V	V	V	V	V	V	V	V	V	V

* Visit 1 and Visit 2 can take place on the same day.

** Subjects who have complete healing during the study or are withdrawn from the study will have all tests scheduled for V14.

¥ Subject do not make a site visit but perform self-dressing.

† Except for Randomization visit, Home Health Care system through study coordinator will be used for those subjects who aren't able to make a visit during the treatment period. Physical examination and measuring weight may be exempt in case of replacing visit with Home Health Care.

- Blood pressure, pulse, body temperature measurement
- Laboratory tests: If test findings within 2 weeks prior to the consent date are available, they may be used instead of screening findings.
 - Hematology: WBC, RBC, platelet, WBC count, Hb, Hct
 - Blood chemistry: AST, ALT, ALP, creatinine, BUN, total bilirubin, glucose, protein, albumin, gamma GTP, TSH (TSH is conducted at screening only)
- Urine hCG pregnancy test is conducted only in women of child-bearing potential.
- The investigational device is changed twice weekly; additional changes are allowed depending on the pressure ulcer condition, without any limitation to frequency.

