5.2 Study objectives

This aim of this study is to exploratively assess the efficacy and safety of hydrophilic polyurethane foam in pressure ulcer patients.

For this purpose, the percentage of completely healed patients and the time to complete healing will be assessed after applying a study device, Medifoam[®] or Betafoam[®], for 12 weeks to pressure ulcer patients. In addition, the pressure ulcer size reduction rate over 12 weeks will be evaluated.

6. Investigational devices

6.1 Study device 1

- Brand name: Betafoam[®] (Mundipharma)
- Generic name: Polyurethane, povidone iodine
- Indications of use: This product is an absorbent foam dressing, used for secondary care of pressure ulcers, venous ulcers, diabetic ulcers, burns, donor sites, bacterial/malignant infection wounds, chronic/acute full/partial thickness losses such as surgical wounds, and wounds with exudates on a thin and rough surface.
- Storage conditions: Store in a sealed container at ambient temperatures (1~30°C), by avoiding direct sunlight and hot and humid conditions.

6.2 Study device 2

- Brand name: Medifoam[®] (Mundipharma)
- Generic name: Polyurethane
- Indications of use: Contamination prevention and protection of wounds
- Storage conditions: Store in a sealed container at ambient temperatures (1~30°C), by avoiding direct sunlight and hot and humid conditions.

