13.1 Betafoam®

A. Contraindications

- (1) Hypersensitivity to povidone iodine included in this product
- (2) In case of rash, pyrexia, allergic reactions or infection symptoms developing while using this product, use of this product is prohibited and appropriate treatment should be instituted as instructed by the physician or pharmacist.
- (3) Thyroid dysfunction (in particular, nodular goiter, endemic goiter, Hashimotos thyroiditis), renal failure, newborns and infants less than 6 months old, herpeticum dermatitis, and before and after radioactive iodine treatment

B. Side effects

Dyspnea, flushing, hives, itching, rash, burning sensation, electrolyte and serum osmotic disorder, temporary renal failure, transient increase in serum protein-bound iodine, pulmonary edema

C. Warning or precautions

- (1) As this product is sterilized, it should be used immediately after opening the package, taking care to avoid contamination of the wound-contacting side.
- (2) This product should be used after consulting a physician or pharmacist.
- (3) In case of development of pruritus (flushing, inflammation), burning sensation, rash, or allergic reactions, consult a specialist.
- (4) Do not use the product if the sterilized pack is already opened or broken.
- (5) In case of severe bleeding, use the product after hemostasis.
- (6) On an infected wound (wound with symptoms such as flare, swelling, pain, feeling hot, strong malodor and pus discharge), use this product after eliminating the cause of bacterial proliferation such as a foreign substance, pus, or necrotized tissue.
- (7) As this product is for single-use only, re-use is prohibited.
- (8) In case of using this product immediately before delivery, wash the eyes of a newborn and bathe him/her as soon as possible after birth.
- (9) In case of using the product in broad burn patients, sufficient hydration should be implemented.
- (10) As this product may influence scintigraphy-based thyroid diagnosis, use of this product and scintigraphy should be separated by 1~2 weeks.

(11) In case of long-term, continuous use of this product, attention should be paid to thyroid dysfunction.

(12) Due to a possibility of a shock (anaphylaxis) in rare cases, in case of sudden development of itching, edema, heartburn, concurrently with severe facial pallor, cold extremities, cold sweat, or shortness of breath after using this product, immediately seek medical attention.

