17.3 Adverse event reporting method

The principal investigator or sub-investigators will inform the subject or guardian of all possible adverse events after the investigational device application, and instruct them to report all events occurring after the study device application.

For all local, systemic, and clinical pathological findings after using the investigational device, the type, onset time, intensity, treatment, drug, course, causal relationship with the investigational device will be recorded and retained in the subject's Case Report Form, according to the Korea Good Clinical Practice for a Medical Device (enforcement date 2016.01.29).

A serious adverse event(SAE) is an adverse event occurring after the investigational device application that corresponds to any of the followings:

- ① Results in death or is life-threatening
- ② Requires inpatient hospitalization or prolongation of existing hospitalization
- ③ Results in persistent or significant disability or dysfunction
- ④ Results in congenital anomaly or birth defect
- ⑤ Other medically important events as identified by the Investigator

In the event that is not included in the above-listed conditions but is thought to likely have a serious influence on the subject's well-being and health in medical aspects, it will be determined whether the event should be considered a serious adverse event at the medical discretion of the investigator and relevant experts, and an appropriate measure will be taken accordingly.

The principal investigator should also review Serious Adverse Event Reports from other sites as notified by the sponsor, and report them according to the SOP of the site IRB.

Unexpected adverse device effect is an event that has a different profile of the adverse device effect or extent of the risk in light of available information on the medical device, such as the Investigator's Brochure or package insert.

All serious and unexpected adverse device effects should be reported within the timeline classified as follows.

<Reporting timeline to the Ministry of Food and Drug Safety>

- (1) In case of a subject's death or seriously life-threatening event during the study, within 7 days after being informed of the event. However, in this case, further information should be additionally reported within 8 days after the initial reporting date.
- (2) For all other serious and unexpected adverse device effects, within 15 days after the sponsor is informed or learned of the event.

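### TSH is measured at screening only, so an asymptomatic thyroid change during up to 12 weeks of a povidone-iodine dressing has no scheduled measurement

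*Protocol*

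**What the plan says.** Section 12.2.2 lists the chemistry analytes tested at screening and at completion or early completion, and ends the list with "TSH (TSH is conducted at screening only". The laboratory footnote to the Schedule of study activities agrees: "gamma GTP, TSH (TSH is conducted at screening only". No other thyroid test appears in the schedule.

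Section 6.1 describes Betafoam as "Generic name: Polyurethane, povidone iodine". Section 13.1 gives as a contraindication "Thyroid dysfunction (in particular, nodular goiter, endemic goiter, Hashimotos thyroiditis", among other conditions, and precaution (11) reads: "In case of long-term, continuous use of this product, attention should be paid to thyroid dysfunction".

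At entry, exclusion 5 in section 8.2 removes subjects with hyperthyroidism, or with a thyroid disorder that needs drug treatment. No TSH cut-off is given.

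After entry, adverse events are reviewed at every weekly visit. Under section 17.3 the investigator "will inform the subject or guardian of all possible adverse events after the investigational device application" and asks for all later events to be reported. Section 12.1.5 adds: "There is no formal limitation in tests to be conducted during an unscheduled visit".

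On who has the Visit 14 tests, footnote ** to the schedule says: "Subjects who have complete healing during the study or are withdrawn from the study will have all tests scheduled for V14". Section 12.1.4 limits early Visit 14 testing to healed subjects, and section 12.2.2 names completion and early completion. Neither mentions withdrawal.

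**The concern.** Thyroid function is the subject of a device-specific precaution, yet TSH is the one chemistry analyte that is not rechecked after exposure. Safety is a stated aim of the study (section 5.2), and section 5.1 says that a further trial will use its results. As written, that trial would inherit no planned thyroid data from Betafoam users.

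A Visit 14 value would feed procedures that already exist: grading for abnormality and clinical significance (section 12.2.2), an adverse event definition that covers abnormal laboratory findings (section 17.1), and follow-up until an event resolves or stabilises (section 17.4). Without it, an asymptomatic change is seen only if someone orders a test for another reason.

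**Working it through.** The plan gives no figure to reproduce. The check compares the schedule with the precaution, then sizes what one added measurement could show.

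**Exposure.** Day 1 to day 85 is 85 − 1 = 84 days, or 84 / 7 = 12 weeks. Subjects who heal early stop sooner, so exposure is up to 12 weeks.

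**Routes to detection, as written**

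| Route | Source | Needs a symptom, sign or other prompt? |
|---|---|---|
| Screening TSH and exclusion 5 | 12.2.2, 8.2 | No, but it precedes exposure |
| Weekly adverse event review; subject or guardian reports | Schedule, 17.3 | Yes |
| Physical examination | Schedule; SAP 7.2 | Yes; may be exempt at home-care visits (protocol), not done at visits outside the site (SAP) |
| Unscheduled or for-cause tests | 12.1.5 | Yes |
| Visit 14 chemistry | 12.1.4, 12.2.2 | No, but TSH is excepted |

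No row gives a scheduled thyroid measurement after baseline. Section 21.13 also expects some subjects with limited communication or cognition, which weakens the routes that depend on reporting.

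**Count of scheduled post-baseline TSH values.** As written: 0 of 10 Betafoam subjects. With TSH on the Visit 14 sample: up to 10 of 10, and at most 20 over both arms.

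**What a clean result would show.** With 0 new abnormalities in n subjects, the exact two-sided 95% upper limit is 1 − 0.025^(1/n):

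- n = 10: 1 − 0.025^(1/10) = 30.8%
- n = 9: 33.6%
- n = 8: 36.9%

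The smaller n apply if subjects are unsampled, or were already abnormal at screening and so cannot contribute a new abnormality.

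**Chance of at least one new abnormality among 10.** The documents give no thyroid event rate, so the rate p is assumed. So is q, the share of changes still present at the draw. The formula is 1 − (1 − pq)^10:

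| Assumed p | q = 1 | q = 0.5 |
|---|---|---|
| 2% | 1 − 0.98^10 = 18.3% | 1 − 0.99^10 = 9.6% |
| 5% | 1 − 0.95^10 = 40.1% | 1 − 0.975^10 = 22.4% |
| 10% | 1 − 0.90^10 = 65.1% | 1 − 0.95^10 = 40.1% |
| 20% | 1 − 0.80^10 = 89.3% | 1 − 0.90^10 = 65.1% |

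**Age of the comparison value.** Results from up to 2 weeks before consent may stand in for screening tests, and the screening window is a further 14 days. The screening TSH can therefore predate first application by about 14 + 14 = 28 days, or 4 weeks.

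**The case against.** The strongest reply is that nothing here is broken. The restriction is worded alike in both places and fits its likely use in applying exclusion 5. The precaution asks for attention, prescribes no test, and leaves prolonged use undefined. The contraindication bears on who should use the product, not on what to measure at the end. Attention is arguably already given through entry screening, weekly event review and unrestricted for-cause testing. All of this stands, and it fixes the point as an optional improvement.

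It also stands that a Visit 14 value fits the precaution imperfectly. The dressing comes off at that visit, so the result can prompt follow-up but cannot inform a decision to stop the dressing in that subject. The detection chances rest on assumed rates and show the scale of what 10 subjects can reveal; they are not a forecast.

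What the reply does not answer is the asymptomatic case. Every existing post-baseline route needs a prompt, while the blood for a scheduled test is already being drawn.

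A reader might infer three stronger claims:

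- *The protocol breaches its own precaution.* The text does not support this, since no test is required and up to 12 weeks may or may not count as prolonged.
- *Thyroid harm would go unseen.* Symptomatic dysfunction has the routes tabulated above.
- *An end-of-study TSH would establish thyroid safety.* With 10 subjects it cannot.

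**Conclusion.** The point holds as an inexpensive improvement to a consistent design choice. The plan schedules no post-baseline thyroid test, so asymptomatic change on Betafoam would not be measured by design. The gain is up to 10 paired TSH values where there would be none, useful as a signal check: even a clean 10 of 10 is compatible with a true rate near 31%.

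The conclusion rests on treating up to 12 weeks as long enough for the precaution to matter, and on sampling most Betafoam subjects at their last visit. It does not rest on the assumed event rates. Efficacy analyses are untouched.

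**What to change.** 1. Delete the screening-only restriction on TSH in the laboratory footnote to the Schedule of study activities and in section 12.2.2, item 2. TSH then runs on the chemistry sample already taken at Visit 14 or early completion.
2. State in sections 12.1.4 and 12.2.2 that withdrawn subjects also have the Visit 14 laboratory tests, to agree with footnote **. Without this, the two deletions do not secure a value at withdrawal.
3. Summarise TSH descriptively as change from screening and as a normal/abnormal shift from screening, so that values abnormal at entry are not counted as new. Protocol section 15.4 and SAP section 8 already cover laboratory summaries. No new SAP row is needed, because Tables 1003 and 1004 show one example analyte and omit the rest. Table 1004 counts abnormal values judged not clinically significant as normal, so read it beside the change in Table 1003.
4. Note topical povidone-iodine use by arm from the concomitant-medication record, since section 10.4 allows it if necessary without restricting it to one arm. Table 0403 reports concomitant medication by arm, but only at ATC levels 1 and 3.

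**Cost.** At most 20 assays on blood already drawn, a few lines of protocol text, one note from data already collected, and an amendment with IRB approval (section 21.2).

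**Limits that remain.** Precision is low; changes that resolve before the draw are missed; early healers are sampled after shorter exposure; permitted povidone-iodine may blur attribution; the screening value may be about 4 weeks old at first application; and an abnormal last-visit value may need follow-up under section 17.4.

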12.2.3 Physical examination

Noticeable findings prior to the investigational device application are recorded in the Medical History section of the Case Report Form, and clinically remarkable physical examination findings after the investigational device application are recorded in the Adverse Event section.

12.2.4 Pressure ulcer assessment

Pressure ulcer assessment during the study based on a scale and the investigator's photo evaluation is to be conducted by the same investigator for the same subject.

(1) Pressure ulcer stage (National Pressure Ulcer Advisory Panel's classification)

Stage	Definition	Description
I	Non-blanchable erythema of intact skin	Intact skin with non-blanchable erythema of a localized area usually over a bony prominence. Discoloration of the skin, warmth, edema, hardness or pain may also be present. Darkly pigmented skin may not have visible blanching
II	Partial thickness skin loss or blister	Partial thickness loss of dermis presenting as a shallow open ulcer with a red pink wound bed, without slough. May also present as an intact or open/ruptured serum or sero-sanguinous-filled blister
III	Full thickness skin loss	Subcutaneous fat may be visible but bone, tendon or muscle are not exposed. Slough may be present. May include undermining and tunneling
IV	Full thickness tissue loss	Full thickness tissue loss with exposed bone, tendon or muscle. Slough or eschar may be present. Often includes undermining and tunneling.

(2) Pressure ulcer assessment time points

At each scheduled visit (once weekly until the End-of-Study visit) from screening to the end of treatment, photograph will be taken to evaluate ulcer size(using a scale) and complete healing status. At baseline, conduct the assessment prior to the investigational device application and subsequently, conduct assessment after completely removing the applied study device and before applying a new dressing.

(3) Measurement of the pressure ulcer size

After removing all dressings applied on the study ulcer, the investigator takes a photograph with a scale measuring the study ulcer size, and records the study ulcer size (surface area of the pressure ulcer) using a scale. At this time, MediRule® will be used as Scale. Width and length are measured using the longest diameter on the pressure ulcer surface area. When taking the photograph, the same illumination, camera model and camera settings should be used for all subjects and a horizontal angle should be maintained between the study ulcer and the camera lens. In addition, manual camera settings should be used to maintain the same settings (such as a shutter speed, aperture, sensitivity, light metering, etc.), and the distance between the study ulcer and the camera focal length should be controlled for each study ulcer, but the same distance should be maintained throughout the study for the same subject. The same scale will be used for assessment of photographs from all subjects. Photographs used for size assessment should be maintained as source documents with subject identification numbers.

(4) Investigator's photo evaluation

The investigator conducts a photo evaluation of the target pressure ulcer, and makes an assessment of the study ulcer size (pressure ulcer surface area) and complete healing status.

(5) Pressure ulcer size and complete healing status documentation**Screening documentation**

Record the pressure ulcer development site, size, the target lesion in case there are multiple pressure ulcer sites, and the NPUAP Stage.

[figure not shown]
* Pressure ulcer size: At screening, record width and length in cm using a scale, to 1 decimal place. Width and length are measured using the longest diameter on the pressure ulcer surface area.

** Target lesion: If there are one or more pressure ulcers, select the largest ulcer of 3 ~ 100 cm² as a target.

(Example of pressure ulcer size measurement recording)

Site of the lesion	Pressure ulcer size		NPUAP Stage	Target lesion (check only 1 among those sized 3~10 cm ²)
	Width	Length		
Coccyx	1.8cm	1.0cm	 1  2  3  4	
Low back	4.7cm	1.0cm	 1  2  3  4	人
Left heel	2.0cm	1.5cm	 1  2  3  4	

(Example of pressure ulcer size measurement for screening)

Documentation at baseline and each visit

In the Case Report Form, the pressure ulcer surface area size based on a scale and the complete healing* status based on the investigator’s photo evaluation will be recorded. As the pressure ulcer surface area size, record **the size of the residual pressure ulcer that has not achieved re-epithelization**** in cm² to 1 decimal place.

Pressure ulcer size: From Visit 2 onwards, the investigator takes a photograph with a scale measuring the study ulcer size and records area (multiplying width and length) in cm using a scale, to 1 decimal place. Width and length are measured using the longest diameter on the pressure ulcer surface area.

(* Complete healing: Defined as the condition with the epithelial tissue covering 100% of the study ulcer, no abrasion or ulceration, intact dermis and epidermis.)

(**Re-epithelization: New epithelial tissue covering the pressure ulcer, with no exudate, transudate, or avascular tissue)

[Example of target pressure ulcer size recording]

	1d (Prior to the study device application, baseline)	8d (Size of a burn lesion with no re-epithelization) (Size of a burn lesion with no re-epithelization)	29d (Size of a burn lesion with no re-epithelization)
Using a scale	5 cm ²	3.5 cm ²	2.2 cm ²	0 cm ²
Investigator’s final photo evaluation	Complete healing  Y  N	Complete healing  Y  N	Complete healing  Y  N	Complete healing  Y  N

(6) Photograph taking and prior meeting

Hold a prior meeting of investigators before study initiation to ensure consistent application during the study period by discussing matters related with the investigator's photo evaluation and photograph taking, such as the camera settings and model, study ulcer and camera focal length, and a scale, etc.

